
1. be at least 18 years of age of either sex and any race;2. provide written informed consent and sign the HIPAA form;3. be willing and able to follow all instructions and attend all study visits;4. (for females capable of becoming pregnant) agree to have urine pregnancy testing performed at screening (must be negative) and at exit visit¹; must not be lactating; and must agree to use a medically acceptable form of birth control² throughout the study duration and for at least 14 days prior to initiation of the investigational product (IP) treatment (Visit 4a) and for one month after cessation of IP treatment. Women considered capable of becoming pregnant include all females who have experienced menarche and have not experienced menopause (as defined by amenorrhea for greater than 12 consecutive months) or have not undergone successful surgical sterilization (hysterectomy, bilateral tubal ligation, or bilateral oophorectomy);5. have a positive history of allergic conjunctivitis and a positive skin test reaction to a [REDACTED] allergen [REDACTED] [REDACTED] Testing will be provided at Visit 1 if the subject has never been tested or if the skin test [REDACTED];6. have a calculated visual acuity of 0.7 logMAR or better in each eye as measured using an ETDRS chart;7. have a positive bilateral CAC reaction³ to allergen within 10 (± 2) minutes of instillation of the last titration of allergen at Visit 2;8. have a positive bilateral CAC reaction⁵ to allergen for at least two out of the three time points following challenge at Visit 3;9. be able and willing to avoid all disallowed medication for the appropriate washout period and during the study (see exclusion 6);10. be able and willing to discontinue wearing contact lenses for at least 72 hours prior to Visit 2 and during the study trial period.
Exclusion Criteria
Subjects may not:

1. have known contraindications or sensitivities to the use of any of the IP treatment or components.

[figure not shown]
¹ The subject must choose an acceptable method of birth control as specified in inclusion criterion d) in order to continue in the study.

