poorly controlled hypertension or poorly controlled diabetes, a history of status asthmaticus, a known history of persistent moderate or severe asthma, or a known history of moderate to severe allergic asthmatic reactions to any of the study allergens;

8. [REDACTED]

9. have planned surgery (ocular or systemic) during the trial period or within 30 days after;

10. have used an investigational drug or medical device within 30 days of the study or be concurrently enrolled in another IP trial;

11. be a female who is currently pregnant, planning a pregnancy, lactating, not using a medically acceptable form of birth control throughout the study duration and for at least 14 days prior to initiation of IP treatment and for one month after cessation of treatment, or has a positive urine pregnancy test at Visit 2;

12. have a history of ocular hypertension (OHT), glaucoma, or an intraocular pressure (IOP) that is less than 8 millimeters Mercury (mmHg) or greater than 22 mmHg in either eye at Visit 2.

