10.3 EXAMINATION PROCEDURES

The following procedures will be conducted at one or more visits, as listed below.

10.3.1 Procedures to be Performed at Each Study Visit with Regard to Study Objective(s)

10.3.1.1 VISIT 1 (Day -50 to -22): Screening / Informed Consent / Skin Test

- *Informed Consent/HIPAA*: Prior to any changes in a subject's medical treatment and/or study visit procedures, the study will be discussed with each subject and subjects wishing to participate must give written informed consent and sign a HIPAA form.

Prior to the completion of Visit 1 (Screening), if it is determined a subject did not in fact meet certain washout criteria, the subject may be brought back at a later date to re-attempt the screening process.

Subjects can be re-screened a maximum of two times.

- *Allergic Skin Test*: A diagnostic test for allergic disease (skin test) will be performed for subjects without documentation of a positive test within the past 24 months.
- *Demographic data and medical/medication/ocular and non-ocular history*: Collect and record all demographic data, medical history, any medications, and any underlying condition(s). Current underlying conditions, including those that began within the last thirty days, which may have been resolved before screening must be recorded. Record any medications the subject is taking, as well as those the subject may have taken but discontinued within 45 days prior to screening.
- *Review of Inclusion/Exclusion Criteria*: Confirm if subject needs to washout from any current medications and instruct he/she to follow the appropriate washout time periods (refer to [Section 10.1.3](#)).
- *Adverse Event Query*: Adverse Events/Adverse Device Effects (both elicited and observed; expected and unexpected; suspected relationship to the treatment, suspected unrelated, and not related) will be monitored throughout the study. All adverse events (both elicited and observed) will be promptly reviewed by the Investigator for accuracy and completeness.
- *Scheduling of Next Visit (Visit 2)*

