10.3.1.2 VISIT 2 (Day -21±3): Titration CAC

- *Update of Medical/Medication History*
- *Adverse Event Query*
- *Urine Pregnancy Test (for females of childbearing potential)*: Women of childbearing potential must have a negative urine pregnancy test to continue in the study and must

agree to use an adequate method of contraception for the duration of the study in order to be enrolled.

- Visual Acuity Utilizing an ETDRS Chart: Subjects must have a score of 0.7 logMAR or better in each eye in order to qualify.
- Initial Ocular and Nasal Allergic Signs and Symptoms Assessment: [REDACTED]
[REDACTED]
[REDACTED]
[REDACTED]
- Slit Lamp Biomicroscopy: A slit-lamp examination will be performed in both eyes to exclude subjects with disallowed ocular conditions. Findings of abnormality which are not exclusionary should be recorded as Medical History.
- Tear Collection: Tears will be collected from up to 60 subjects to ensure there are enough potential subjects at Visit 3 for the confocal microscopy subset. If 5 μ l of tears is not collected at Visit 2, the subject will not have any additional tears collected for this trial and will not be a member of the confocal subset. The technician collecting tears will note the subject's reflex tearing, if applicable (see **Appendix 2**). There will be at least a 30 minute wait period between Tear Collection and the Titration CAC.
- Review of Inclusion/Exclusion Criteria: A review of protocol inclusion and exclusion criteria will be confirmed for each subject.
- Titration Conjunctival Allergen Challenge (CAC): A [REDACTED]
[REDACTED]
[REDACTED]
[REDACTED]
■ [REDACTED]
[REDACTED]
[REDACTED]
[REDACTED]
[REDACTED]
■ [REDACTED]
[REDACTED]
[REDACTED]
[REDACTED]
- Post-CAC Ocular and Nasal Allergic Signs and Symptoms Assessment: Upon completion of the initial titration CAC, subjects will receive an ocular examination by the Investigator to evaluate all Investigator-evaluated efficacy measures and confirm

the subject's qualification. Subjects will be asked to assess their ocular and nasal symptoms.

- IOP Measurement: Intraocular Pressure (IOP) will be measured in each eye by contact tonometry, for qualified subjects.
- Dilated Ophthalmoscopy: A dilated ophthalmoscopy will be performed by the Investigator to evaluate the presence or absence of clinically significant fundus abnormalities and vitreous pathology, for qualified subjects.
- Review of Inclusion/Exclusion Criteria

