- **Diary Dispensation:** The subset of subjects undergoing tear collection and confocal microscopy will be dispensed a diary to complete daily assessments prior to bedtime on the evening of Visit 3 and upon awakening the next morning. Subjects will be given a mailing label and instructed to mail the diary back to the site following their morning assessments.
- **Tear Collection:** Tears (5 μ L from each eye) will be collected from the confocal subset at 2 (+1) hours after instillation of the anesthetic used for confocal microscopy procedures. If 5 μ L of tears from each eye is not collected, the subject will remain in the confocal microscopy subset but no further tear collections will be performed. The technician collecting tears will note the subject's reflex tearing, if applicable (see **Appendix 2**).
- **Review of Inclusion/Exclusion Criteria**
- **Relief Drop Instillation:** Subjects may receive a dose of a currently marketed, topical ophthalmic anti-allergic agent (i.e., anti-histamine/vasoconstrictor combination products like Visine®-A®) as they leave the office to relieve any immediate discomfort caused by the allergic reaction.
- **Adverse Event Query**
- **Schedule (Visit 4a):** Subjects will be asked to return to the office 7 days later for Visit 4a, the Duration of Action Visit.

¹⁴ Not necessarily at the same time point

10.3.1.4 VISIT 4a (Day 1): 1st Dose, Enrollment / Randomization to PRT-2761, PV or Patanol® & in-office instillation

- Update of Medical/Medication History
- Adverse Event Query
- Assessments Diary Review and Collection: Diary will be collected (if not mailed in) and reviewed.
- Visual Acuity Utilizing an ETDRS Chart: A clinically significant visual acuity decrease (defined as an increase of 0.22 or greater in logMAR score) from Visit 2 will be considered an adverse event.
- Pre-CAC Ocular and Nasal Allergic Signs and Symptoms Assessment: [REDACTED]
[REDACTED]
[REDACTED]
[REDACTED]
[REDACTED]
- Slit Lamp Biomicroscopy
- Review Inclusion and Exclusion Criteria

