10.3.1.9 VISIT 6b (8 [+1] Hours post-Visit 6a,): 5th Dose/CAC #5

- Update of Medical/Medication History
- Adverse Event Query
- Visual Acuity Utilizing an ETDRS Chart: A clinically significant visual acuity decrease (defined as an increase of 0.22 or greater in logMAR score) from Visit 2 will be considered an adverse event.
- Pre-CAC Ocular and Nasal Allergic Signs and Symptoms Assessment
- Slit Lamp Biomicroscopy
- Investigational Product Instillation: [REDACTED]
[REDACTED]
[REDACTED]
- Conjunctival Allergen Challenge (CAC): [REDACTED]
[REDACTED]
[REDACTED]
- Post-CAC Ocular and Nasal Allergic Signs and Symptoms Assessment: Assessment of itching will be made by the subject at 5(±1), 7(±1), 10(±1), 15(±1), 20(±1), 25(±1), and 30(±1) minutes following allergen challenge. Assessments of redness and chemosis will be graded by the Investigator at 7(±1), 15(±1), 20(±1), 25(±1) and 30(±1) minutes post-challenge. Assessments of eyelid swelling, tearing/watery eyes, and nasal symptoms will be made by the subject at 7(±1), 15(±1), 20(±1), 25(±1), and 30(±1) minutes post-challenge (**Appendix 2**).

- *Diary Dispensation*: All subjects will be dispensed a diary to complete daily assessments prior to bedtime and upon awakening until the morning of Visit 7. Subjects will be instructed to bring the diary to the next visit (Visit 7) for a compliance check.
- *Ora Photography System*: The subset of subjects who underwent confocal microscopy will be dispensed cameras for at home assessments, to be done alongside diary assessments.
- *Adverse Event Query*
- *Scheduling of next visit (Visit 7)*: Subjects will be asked to return to the office the following day (Day 17) Visit 7.

10.3.1.10 Visit 7(24 hours (± 6 hrs) Post-Dose at Visit 6a): 6th Dose/CAC #6

- *Update of Medical/Medication History*
- *Adverse Event Query*
- *Assessments Diary Review and Collection*: Assessments diary will be collected and reviewed for compliance from Visit 6b to Visit 7 and to address any queries.
- *Urine Pregnancy Testing*: This will be given to all women of childbearing potential
- *Visual Acuity Utilizing an ETDRS Chart*: A clinically significant visual acuity decrease (defined as an increase of 0.22 or greater in logMAR score) from Visit 2 will be considered an adverse event.
- *Pre-CAC Ocular and Nasal Allergic Signs and Symptoms Assessment*
- *Slit Lamp Biomicroscopy*
- *Digital Imaging*: Digital photographs may be taken of each eye.
- *Investigational Product Instillation*: [REDACTED]

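### Women of childbearing potential get their first dose on a pregnancy test that is 18 to 24 days old, with no re-test at Visit 4a

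*Protocol*

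**What the plan says.** Protocol 7.3, inclusion 4 (also in the synopsis), requires that women capable of becoming pregnant "agree to have urine pregnancy testing performed at screening (must be negative) and at exit visit". It also requires acceptable contraception throughout the study, for at least 14 days before first treatment and for one month after the last.

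Protocol 7.4, exclusion 11, bars anyone who would "be a female who is currently pregnant, planning a pregnancy, lactating", and adds "or has a positive urine pregnancy test at Visit 2". That is the only test result the criterion names.

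The visit procedures in Protocol 10.3.1 agree with this:

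- Visit 1 is headed "VISIT 1 (Day -50 to -22): Screening / Informed Consent / Skin Test" and lists no pregnancy test.
- Visit 2 (Day -21 ±3): "Women of childbearing potential must have a negative urine pregnancy test to continue in the study".
- Visit 3 lists none.
- Visit 4a (Day 1) updates the history, repeats visual acuity and slit lamp, and has the item "Review Inclusion and Exclusion Criteria". It then goes to randomisation and the first instillation. No pregnancy test is listed.
- Visits 4b to 6b list none.
- Visit 7 lists a urine test before that visit's instillation: "This will be given to all women of childbearing potential".

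Protocol 10.4.2 allows pregnancy testing at unscheduled visits but does not require it. The synopsis says that PRT-2761 has no prior human use and was safe and well tolerated in animal studies.

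**The concern.** Current pregnancy is an exclusion, and Protocol 10.1.4 requires every criterion to be met for enrolment. At Day 1 that criterion is checked without a current test. The history update and eligibility review can find only a pregnancy the woman already knows about.

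Two kinds of pregnancy would pass through to dosing: one too early to show at Visit 2, and one conceived after Visit 2. The first is possible even in a woman who follows every rule. Contraception for the study's duration appears to start at Visit 1, but Visit 1 may fall only one day before Visit 2.

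What is at stake is participant safety, namely fetal exposure to a compound with no human data. No estimate, test or sample size is affected.

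**Working it through.** The documents state no figure for the age of the test, so there is none to reproduce. The check is calendar arithmetic.

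**Inputs.** Visit 1 is Day -50 to -22, Visit 2 is Day -21 ±3 and Visit 3 is Day -14 ±3 (Protocol 10.3.1). First dose is Visit 4a, Day 1. Visit 5a is Day 15 ±3, and Visit 7 is two days after Visit 5a. SAP 3.1 states there is no Day 0, so Day -d is d days before Day 1.

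**Age of the negative result at first dose**

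| Visit 2 on | Days to Day 1 |
|---|---|
| Day -24 | 24 |
| Day -21 (planned) | 21 |
| Day -18 | 18 |

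**Alternative reading.** The Visit 3 scheduling item says "Subjects will be asked to return to the office 7 days later for Visit 4a". This conflicts with the day numbering, which puts 14 days (11 to 17) between Visits 3 and 4a. If the sentence is followed:

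- Visit 2 to Visit 3 is 7 days nominal, from 1 (Day -18 to -17) to 13 (Day -24 to -11).
- Adding 7 gives a test age of 14 days nominal, range 8 to 20.

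The result is still not current at dosing.

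**First dose to next scheduled test.** Day 1 to Day 17 is 16 days. With Visit 5a at Day 12 or Day 18, Visit 7 falls at about Day 14 or Day 20, which gives 13 to 19 days. The doses at 4a, 5a, 5b, 6a and 6b come before that test: five of six.

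**Visit 1 to Visit 2.** The shortest gap is Day -22 to Day -21, 1 day. The longest is Day -50 to Day -18, 32 days.

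**Likely number of events (illustration only).** Protocol 9.1.1 gives 30 + 30 = 60 subjects on PRT-2761, out of 120. The documents do not say how many are women of childbearing potential. Assume 30% to 50% of the 60, that is 18 to 30 women, and a contraceptive failure rate of 1% to 10% per year. Expected new conceptions in 21 days = women × annual rate × 21/365:

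- low: 18 × 0.01 × 21/365 = 0.010
- high: 30 × 0.10 × 21/365 = 0.173

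Pregnancies already present but too early to show at Visit 2 would add to this. The documents give no basis for a number.

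**The case against.** The provisions are consistent with each other, and nothing in the documents sets a maximum age for the test. The existing controls are layered: a negative test to pass Visit 2, exclusion of women who are pregnant or planning pregnancy, defined contraception covering the interval to first dose, an eligibility review at Visit 4a, and follow-up of any positive test. Exposure is six in-office eye-drop administrations, and the last five fall within about 48 hours. The readable text gives no reproductive-toxicity or systemic-exposure data either way.

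The expected count is small and rests on assumptions. A Visit 4a test would also miss the most recent conceptions. If the last 7 to 14 of the 21 days cannot be detected (a further assumption), the detectable share falls to between 18 × 0.01 × 7/365 = 0.003 and 30 × 0.10 × 14/365 = 0.12.

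Finally, the Appendix 1 schedule cannot be read, and a Visit 4a test could be listed there.

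Most of this stands as context. The event is unlikely, this is a design choice rather than a contradiction, and the numerical benefit cannot be established from the documents. It does not close the gap. Contraception lowers the chance of pregnancy without establishing status at dosing, unscheduled testing is optional, and follow-up of a positive test at Visit 7 comes after exposure. The detectable-share argument also leaves out pregnancies too early for Visit 2, which a test about three weeks later is better placed to find. A hidden Visit 4a test in Appendix 1 is possible, but inclusion 4, exclusion 11 and the readable Visit 4a headings all point the other way.

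**Conclusion.** The point holds. By the protocol's day numbering, the only scheduled pregnancy test before dosing is 21 days old at first dose (18 to 24). Under the conflicting Visit 3 sentence it is 14 days old (8 to 20). The current-pregnancy exclusion is therefore reviewed at Visit 4a without a test to support it, before a drug with no prior human use. The gap applies to every randomised woman of childbearing potential. Of the 120 planned subjects, 60 receive PRT-2761.

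The probability of an event is low, at about 0.01 to 0.17 new conceptions under the stated assumptions. The recommendation rests on the consequence and the small cost of prevention. It assumes that the unreadable Appendix 1 agrees with the visit lists; a Visit 4a test scheduled there would remove the point.

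**What to change.** Add the existing urine pregnancy test to the Visit 4a procedures for women of childbearing potential, as part of the eligibility review and before randomisation. The result would then be 0 days old at first dose. To match:

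- amend inclusion 4 (synopsis and 7.3) so that testing is at screening and at Visit 4a, both negative, and at exit;
- amend exclusion 11 (synopsis and 7.4) to cover a positive urine test at Visit 2 or Visit 4a;
- make sure Appendix 1 shows the same.

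The cost is one more kit, of a type the sponsor already supplies (Protocol 9.2), and a few minutes per woman at a visit that already reviews eligibility. There may be an occasional late screen failure, but such a woman is already ineligible under exclusion 11. No endpoint, sample size or analysis changes.
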